6.3.3. Study treatment compliance and exposure

The following analyses will be based on the Safety population.

Compliance will be calculated using subject's diary by dividing doses taken by doses planned.

Compliance will be summarized by visit and will also be a factor in defining the PP population as noted in Section 4.3.1.

Listings of baseline study drug application, study drug accountability, compliance, and study drug interruption will be created.

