9.2 Treatment Compliance

Subjects will be required to return the IP tubes that are used and/or unused. Each subject will be instructed on the importance of both the application of the IP and return of the used and unused IP tubes. Each tube will be weighed when returned and the results will be entered on the source document and eCRF.

Patients will be dispensed a diary to maintain a log of their IP application. Any interruptions in the schedule of IP administration or use of prohibited concomitant medication will be recorded in the eCRFs.

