5. GENERAL METHODOLOGY AND CONVENTIONS

5.1. Sample size determination

As stated in the CSP, this study is not powered for statistical significance. Eligible subjects (completers) from PellePharm Studies 926-201 and 926-301 will be enrolled into this study up to a maximum of about 200 participants.

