6. ANALYSES AND SUMMARIES

6.1. Primary Endpoints

6.1.1. Safety and Tolerability.

Safety and tolerability are the primary objectives of this study and will be evaluated by reviewing adverse events (see Section 6.4.2), treatment discontinuations and dermal safety and tolerability (see Section 6.4.1).

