6.1.1.1. Primary analysis

No inferential tests will be performed. Data will be summarized through descriptive statistics only.

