6.4.1. Dermal Safety and Tolerability

Dermal safety and tolerability will be evaluated through assessment of selected local signs and symptoms (pain/burning, pruritus, erythema, edema, and crusting) on the face. Any local skin reaction that requires use of a concomitant therapy or causes interruption or discontinuation of the IP should be reported as a dermal safety event. These events will be assessed for severity, relative to the skin reactions scale.

Shift tables of the frequency of dermal safety and tolerability assessments including pain/burning, pruritus, erythema, edema, and crusting will be summarized using counts and percentages by visit compared to baseline.

A listing of all dermal safety and tolerability assessments will be also provided.

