6.4.2. Adverse Events

AEs will be graded by the investigator and coded using most recent version of the Medical Dictionary for Regulatory Activities (MedDRA).

Treatment-emergent adverse events (TEAEs) are those events with onset dates occurring during the on-treatment period for the first time, or if the worsening of an event is during the on-treatment period.

All analyses described **Error! Reference source not found.** will be based on TEAEs (started during the on-treatment period) if not otherwise specified. The AE listings will include all AEs (whether treatment-emergent or not). AEs outside the on-treatment period will be flagged in the listings.

- Related Adverse Events: adverse events with relationship to study treatment (as recorded on the AE eCRF page, Relationship with study treatment = Possibly / Probably / Definitely) reported by the investigator and those of unknown relationship (i.e., no answer to the question 'Relationship with study treatment'). Related AEs are those related to any study treatment.
- **Serious Adverse Events (SAE):** serious adverse events (as recorded on the AE eCRF page, Serious Adverse Event = Yes).
- Adverse Events Leading to Permanent Treatment Discontinuation: adverse events leading to permanent discontinuation of study treatment (as recorded on the AE eCRF page, Action taken with study treatment = Drug withdrawn).

• Adverse Events Leading to Death: adverse event leading to death (as recorded on the AE eCRF page, Outcome = Fatal).

Unless otherwise specified, AEs will be summarized by number and percentage of patients with the AE in the category of interest as described above, by primary SOC and PT in decreasing frequency based on the frequencies observed.

Each patient will be counted only once within each SOC or PT. If a patient experiences more than one AE within a SOC or PT for the same summary period, only the AE with the strongest relationship or the worst severity, as appropriate, will be included in the summaries of relationship and severity.

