6.4.2.1. All adverse events

Adverse events will be summarized by worst severity per patient, using the latest version of MedDRA preferred term (PT) as event category and MedDRA primary system organ class (SOC) body term as Body System category.

In case a patient has events with missing and non-missing severity, the maximum of the non-missing severity will be displayed. No imputation of missing severity will be performed.

AEs will be split between "prior to treatment" and "treatment emergent". The following tables will be created:

- The overall summary of AEs table will include the frequency (number and percentage) of patients with each of the following:
 - TEAEs
 - TEAEs related to IP
 - TEAEs leading to treatment discontinuation
 - TEAEs related to IP leading to treatment discontinuation
 - Paralesional TEAEs
 - Serious TEAEs
 - Serious TEAEs related to IP
 - TEAEs leading to death
 - TEAEs related to IP leading to death
- TEAEs by SOC and PT and maximum severity
- TEAEs by closest relationship to study drug

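### No planned table identifies TEAEs or dermal safety events that led to interruption of the gel, although interruption is part of the SAP's own definition of a dermal safety event

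*SAP*

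**What the plan says.** SAP 6.1.1 and Protocol section 6 evaluate the primary objective through adverse events, discontinuations of treatment, and dermal safety and tolerability. SAP 6.1.1.1 adds: "No inferential tests will be performed. Data will be summarized through descriptive statistics only".

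- **Adverse events.** SAP 6.4.2 defines four categories of interest: related, serious, leading to permanent discontinuation, and leading to death. The only one defined by what was done with the gel is identified by "Action taken with study treatment = Drug withdrawn". The overall table in SAP 6.4.2.1 carries "TEAEs leading to treatment discontinuation" and the same row restricted to related events. SAP 6.4.2.2 adds an SOC/PT table for discontinuation.
- **Dermal events.** On facial skin reactions, SAP 6.4.1, which follows Protocol 8.3.1, says of any such reaction when it is severe enough to affect care: one which "requires use of a concomitant therapy or causes interruption or discontinuation of the IP should be reported as a dermal safety event". The planned outputs are shift tables of the five sign and symptom scores by visit, and a listing of assessments.
- **Interruption.** SAP 6.3.3: "Listings of baseline study drug application, study drug accountability, compliance, and study drug interruption will be created". The same section summarises diary compliance by visit.
- **Data collection.** Protocol 9.2: "Any interruptions in the schedule of IP administration or use of prohibited concomitant medication will be recorded in the eCRFs". Protocol 11.1.2 collects the action taken with the IP for every AE.

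**The concern.** A patient on a self-applied gel can stop for a time, let a reaction settle and start again. Such a patient has had a tolerability problem that changed treatment, yet never becomes a discontinuation. Permanent stopping gets a disposition count, a Kaplan-Meier curve, two rows in the overall table and an SOC/PT table. Temporary stopping gets a listing.

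With no test or model to follow, a reader of the study report judges tolerability from these tables. If interruptions are at all common, that reader cannot see from any summary how many patients had to pause the gel because of an event, or which events caused it. The gap is sharpest for skin reactions, where both documents treat interruption as making the reaction reportable and the SAP then does not count the reportable event.

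**Working it through.** The plan states no figure to reproduce. The check is a tally of planned outputs, followed by a test of whether another output fills the gap.

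**1. Tally of safety outputs (SAP 6.3.3 and 6.4)**

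| Output | On discontinuation | On interruption |
|---|---|---|
| AE categories of interest, 6.4.2 (4 defined) | 1 | 0 |
| Rows of overall AE table, 6.4.2.1 (9 rows) | 2 | 0 |
| SOC/PT tables by action taken, 6.4.2.2 | 1 | 0 |
| Listings naming drug interruption, 6.3.3 | – | 1 |
| Counts of dermal safety events by trigger, 6.4.1 | 0 | 0 |

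**2. Do the all-TEAE tables fill the gap?** In part. They count every TEAE by SOC, PT, severity and relationship whatever was done with the gel, so a reported event that led to a pause is included but cannot be recognised as such.

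**3. Will a skin reaction that only interrupts the gel be reported as an AE?** Not certainly. Protocol 8.3.1 lists three triggers: concomitant therapy, interruption, and discontinuation of the IP. Protocol 11.1.2 sends dermal findings to AE reporting for two: concomitant therapy, and discontinuation from the study. The general AE definition in Protocol 11.1.1 is broad enough to cover the reaction, but the specific dermal rule does not require it to be reported.

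**4. Do the dermal shift tables fill the gap?** Table 1 of the protocol schedules dermal scoring at Baseline and Months 3, 6, 9 and 12.

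- Erythema, edema and crusting are scored as seen by the investigator. With the SAP 5.2.4 conversion, a quarter is 3 × 30.4375 = 91.3 days. If a reaction lasts *d* days and begins at a random time in the quarter, the chance that it is present at the next scoring is *d* / 91.3. For assumed durations of 7, 14 and 21 days this gives 7/91.3 = 7.7%, 14/91.3 = 15.3% and 21/91.3 = 23.0%.
- Pain/burning and pruritus are recalled at their worst since the last visit, so this calculation does not apply to them. Their scores still do not show whether application stopped.

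**5. Does the compliance summary fill the gap?** It divides doses taken by doses planned and carries no cause. The SAP does not say whether doses during a pause count as planned. Take a 21-day pause in an otherwise fully compliant patient:

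- Pause counted as planned, one quarter: (91.3 − 21)/91.3 = 77.0%.
- Pause counted as planned, 12 months: (365.25 − 21)/365.25 = 94.3%, well inside the 80% to 120% range in SAP 4.2.1.
- Pause not counted as planned: 100%.

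A by-visit figure may therefore show a dip. It cannot separate an adverse reaction from forgotten doses.

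**The case against.** The case for leaving the plan alone has real strength.

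- *A reader might infer that the SAP tabulates only events that stop the gel for good, and that interrupting events appear nowhere but a listing.* The documents do not support that. All TEAEs are tabulated, and Protocol 12.7.2 lists the action taken for each AE. What is missing is the label in a summary.
- *A reader might infer that the SAP drops a component of the primary evaluation.* It does not. Both documents name discontinuations there, not interruptions. The gap is narrower: dermal safety is a named component, and the SAP's own definition of a dermal safety event includes interruption.
- *A reader might infer that dermal safety events are never counted.* That is too strong. Those needing concomitant therapy or leading to discontinuation from the study become AEs under Protocol 11.1.2 and enter the TEAE tables. The reaction that only interrupts treatment is the exposed case.
- Patients with an AE may attend an unscheduled visit with the same assessments (Protocol 8.1.9). That helps less than it seems: SAP 5.2.5 assigns such data to the nearest visit for summary, while SAP 5.2.3 says safety data from unscheduled visits are listed and not summarised.
- The only action-taken value the SAP quotes is the one for withdrawal. Whether the eCRF has a value for interruption cannot be seen from the documents. This stands and is carried into the fix.

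**Conclusion.** The point holds as a gap in reporting. No planned summary identifies patients whose TEAE or skin reaction led to interruption, and the dermal safety event that SAP 6.4.1 defines is not counted as such. The structural size is 0 of 9 overall AE rows, 0 of 4 AE categories and 0 dermal event counts, against one listing.

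The number of patients affected is unknown. Neither document gives an interruption rate, so any contrast between a percentage who stop and a percentage who stop or pause would be invented, and none is offered. The 8% to 23% chance in the working rests on assumed reaction durations of 7 to 21 days with random onset, and applies only to erythema, edema and crusting.

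This does not invalidate the planned analysis. It is an inexpensive addition that makes the descriptive primary result more complete.

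**What to change.** 1. **SAP 6.4.1:** add the number and percentage of patients with at least one dermal safety event, overall and by trigger (concomitant therapy, interruption, discontinuation). A patient may have more than one trigger, so the rows need not sum to the total. State which eCRF fields identify the event and its trigger.
2. **SAP 6.4.2.1:** add one row for TEAEs leading to interruption and one for IP-related TEAEs leading to interruption, from the action-taken field. First confirm that the eCRF field has that value.
3. **SAP 6.3.3:** add the number and percentage of patients with any interruption, with the number of interruptions and days interrupted, from the records required by Protocol 9.2. State whether doses during a pause count as planned in the compliance ratio.
4. **Reconcile** Protocol 8.3.1 and SAP 6.4.1 with Protocol 11.1.2 on which dermal events are reported as AEs. Until that is done, the rows in item 2 may miss reactions that only interrupted the gel, which is why items 1 and 3 are needed as well.

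The cost is SAP wording, a protocol clarification and a few tables, using data that the protocol says are collected, subject to the field check. The downside is some programming and a tolerability picture that may look less favourable.

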6.4. Safety Summaries and Analyses

The Safety Population will be the primary population for safety evaluations. All summaries of AEs and other safety parameters will be based on the safety population.

6.4.1. Dermal Safety and Tolerability

Dermal safety and tolerability will be evaluated through assessment of selected local signs and symptoms (pain/burning, pruritus, erythema, edema, and crusting) on the face. Any local skin reaction that requires use of a concomitant therapy or causes interruption or discontinuation of the IP should be reported as a dermal safety event. These events will be assessed for severity, relative to the skin reactions scale.

Shift tables of the frequency of dermal safety and tolerability assessments including pain/burning, pruritus, erythema, edema, and crusting will be summarized using counts and percentages by visit compared to baseline.

A listing of all dermal safety and tolerability assessments will be also provided.

6.4.2. Adverse Events

AEs will be graded by the investigator and coded using most recent version of the Medical Dictionary for Regulatory Activities (MedDRA).

Treatment-emergent adverse events (TEAEs) are those events with onset dates occurring during the on-treatment period for the first time, or if the worsening of an event is during the on-treatment period.

All analyses described **Error! Reference source not found.** will be based on TEAEs (started during the on-treatment period) if not otherwise specified. The AE listings will include all AEs (whether treatment-emergent or not). AEs outside the on-treatment period will be flagged in the listings.

- Related Adverse Events: adverse events with relationship to study treatment (as recorded on the AE eCRF page, Relationship with study treatment = Possibly / Probably / Definitely) reported by the investigator and those of unknown relationship (i.e., no answer to the question 'Relationship with study treatment'). Related AEs are those related to any study treatment.
- **Serious Adverse Events (SAE):** serious adverse events (as recorded on the AE eCRF page, Serious Adverse Event = Yes).
- Adverse Events Leading to Permanent Treatment Discontinuation: adverse events leading to permanent discontinuation of study treatment (as recorded on the AE eCRF page, Action taken with study treatment = Drug withdrawn).

• Adverse Events Leading to Death: adverse event leading to death (as recorded on the AE eCRF page, Outcome = Fatal).

Unless otherwise specified, AEs will be summarized by number and percentage of patients with the AE in the category of interest as described above, by primary SOC and PT in decreasing frequency based on the frequencies observed.

Each patient will be counted only once within each SOC or PT. If a patient experiences more than one AE within a SOC or PT for the same summary period, only the AE with the strongest relationship or the worst severity, as appropriate, will be included in the summaries of relationship and severity.

6.4.2.1. All adverse events

Adverse events will be summarized by worst severity per patient, using the latest version of MedDRA preferred term (PT) as event category and MedDRA primary system organ class (SOC) body term as Body System category.

In case a patient has events with missing and non-missing severity, the maximum of the non-missing severity will be displayed. No imputation of missing severity will be performed.

AEs will be split between "prior to treatment" and "treatment emergent". The following tables will be created:

- The overall summary of AEs table will include the frequency (number and percentage) of patients with each of the following:
 - TEAEs
 - TEAEs related to IP
 - TEAEs leading to treatment discontinuation
 - TEAEs related to IP leading to treatment discontinuation
 - Paralesional TEAEs
 - Serious TEAEs
 - Serious TEAEs related to IP
 - TEAEs leading to death
 - TEAEs related to IP leading to death
- TEAEs by SOC and PT and maximum severity
- TEAEs by closest relationship to study drug

6.4.2.2. Adverse events leading to discontinuation of study treatment

The frequency (number and percentage) of patients TEAEs leading to discontinuation of Patidegib will be tabulated by SOC and PT.

A listing of all AEs leading to treatment discontinuation will also be provided with the relevant information.

6.4.2.3. Deaths

The frequency (number and percentage) of patients in the safety analysis set who died will be tabulated based on information from the 'End of Treatment', 'End of Study' and 'Adverse Event Log' eCRF pages.

6.4.2.4. Serious Adverse Events

The frequency (number and percentage) of patients with each of the following will be presented for treatment-emergent SAEs:

- SAEs by SOC and PT
- Related SAEs by SOC and PT

The listings of all SAEs will also be provided with the relevant information with a flag for SAEs with onset outside of the on-treatment period.

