11.1.3 Serious Adverse Events

All AEs will be assessed as either serious or non-serious.

An SAE or serious adverse reaction is defined as any untoward medical occurrence that at any dose:

- Results in death
- Is immediately life threatening, (the term "life threatening" in the definition of "serious" refers to an event in which the subject is at risk of death at the time of the event; it does not refer to an event which hypothetically might have caused death if it were more severe)
- Requires in-patient hospitalization or prolongation of existing hospitalization (hospitalization for elective surgery for a condition present at Screening is not considered an AE)
- Results in persistent or significant disability/incapacity (permanent or substantial disruption of a person's ability to conduct normal life functions)
- Is a congenital anomaly/birth defect
- Is a medically important event that may not be immediately life threatening or result in death or hospitalization, but may jeopardize the subject and may require medical or surgical intervention to prevent any of the above listed outcomes

If the BCC surgery requires, as per standard of care, that the patient be hospitalized, then this hospitalization is not an SAE.

Note: A spontaneous abortion will be considered an SAE and must be reported per Reporting of SAEs under Section 11.1.6. Pregnancy in and of itself is not an SAE, but a subject who becomes pregnant must discontinue IP application immediately and the pregnancy will be followed to term (and ideally the child will be followed afterward if the subject consents) or termination. Any birth defect or other serious issue that may arise during the pregnancy or due to fetal exposure will be considered an SAE.

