12.7.2 Adverse Events

Subjects will be assessed for the occurrence of new and ongoing AEs. Listings of AEs will include the dates of onset and resolution (if resolved), maximum severity, seriousness, action taken regarding the IP, corrective treatment, outcome, and Investigator's assessment of causality. All AEs will be recorded and classified using terminology from the MedDRA. All reported TEAEs, defined as any AE with an onset on or after the date of first IP application, or worsening of an AE with an onset prior to first IP application, will be summarized, the number of subjects reporting TEAEs, system organ class, preferred term, severity, and relationship to IP. When summarizing TEAEs by severity or relationship to IP, each subject will be counted only once within a system organ class or a preferred term using the event with the greatest severity or causality, respectively, within each category. All reported SAEs will be summarized, the number of subjects reporting SAEs, system organ class, preferred term, severity, and relationship to IP.

All information pertaining to AEs noted during the study will be listed by subject and will include a verbatim description of the event as reported by the Investigator, as well as the preferred term, system organ class, start date, stop date (if stopped), seriousness, severity, action taken regarding the IP, corrective treatment, outcome and relationship to the IP. In addition, a listing of subjects who prematurely discontinue from the study due to AEs will be provided as well as a listing of subjects who reported an SAE.

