5.2.3. Definition of on-treatment period

Safety endpoints will be summarized based on the on-treatment period unless otherwise specified.

On-treatment period is defined as the time from the first IP application of study treatment to last IP application of study treatment + 30 days.

Safety data collected outside the on-treatment period as well as data from unscheduled visits will be listed and flagged in listings but not summarized.

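### The protocol promises a summary of all reported SAEs, but the SAP's SAE tables stop at last application + 30 days and leave out SAEs before the first dose

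*SAP*

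**What the plan says.** Protocol 12.7.2 (Adverse Events) sets the scope of the SAE summary: "All reported SAEs will be summarized, the number of subjects reporting SAEs, system organ class, preferred term, severity, and relationship to IP". It states no time limit. The TEAE definition in the same section, "any AE with an onset on or after the date of first IP application" (or worsening of an earlier event), has a start but no end.

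The SAP, which by its section 2 takes precedence over the protocol's statistical plans, sets narrower limits:

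- SAP 5.2.3: the on-treatment period runs from first application "to last IP application of study treatment + 30 days". Safety data outside it "will be listed and flagged in listings but not summarized".
- SAP 6.4.2: TEAEs are events with "onset dates occurring during the on-treatment period for the first time, or if the worsening of an event is during the on-treatment period".
- SAP 6.4.2.1: the serious rows of the overview table are serious TEAEs and related serious TEAEs. AEs are divided into those before treatment and those that are treatment-emergent, with no post-treatment group.
- SAP 6.4.2.4: SAEs by SOC and PT, and related SAEs by SOC and PT, "will be presented for treatment-emergent SAEs". A listing of all SAEs flags those with onset outside the on-treatment period.
- SAP 6.4.2.3: deaths in the safety set are tabulated without reference to the window.

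The protocol itself foresees late SAEs. Under 11.1.3 a subject who becomes pregnant "must discontinue IP application immediately and the pregnancy will be followed to term" or termination, and a spontaneous abortion or birth defect is an SAE. Under 11.1.6 related SAEs must be reported to the safety database however long after the last dose they occur.

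**The concern.** Safety is the primary objective, and SAEs are its most closely read component. The protocol's commitment covers all reported SAEs. The SAP replaces it with a windowed subset and does not identify or explain the change. Two groups lose their place in the tables: SAEs after consent but before first application, and non-fatal SAEs that first arise more than 30 days after the last application.

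The second group matters more. Embryo-fetal toxicity in non-clinical studies is the stated reason for the contraception rules (Protocol 6.1). Because the gel stops as soon as pregnancy is known, many pregnancy outcomes would occur well after the window closes. The SAEs closest to the known hazard are thus among those most likely to be left out of the tables.

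**Working it through.** The plan states no figure to reproduce. The check is a trace through the text, followed by arithmetic on timing and frequency under stated assumptions.

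**Trace by time of onset**

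- *Consent to first application.* The SAE is recorded (Protocol 11.1.2 and 11.1.6). It is not a TEAE unless it worsens in the window, so it is in neither SAE table nor the serious overview rows.
- *First application to last application + 30 days.* It is counted in the SAP tables.
- *After last application + 30 days, non-fatal.* It is not a TEAE and is in no SAE table. It reaches the flagged listing only if it is in the clinical database. Protocol 11.1.6 describes eCRF capture for the study's duration and 30 days after last application. Protocol 11.1.2 calls the 30-day follow-up visit a minimum. Later eCRF entry is therefore uncertain.
- *Exceptions.* A late death is counted in SAP 6.4.2.3, though without relationship. An SAE with no onset date at all is set to treatment start (SAP 5.3.2.1) and so is counted.

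Pregnancy is not the only route. The follow-up visit falls 30 days after the Exit Visit (Protocol Table 1, note d), while the SAP window runs from last application. If the last application is *k* days before the Exit Visit, the follow-up visit is at last application + 30 + *k* days. An SAE arising in those last *k* days is duly recorded but not tabulated.

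**Timing of pregnancy outcomes** (assumptions: gel stopped at gestational week 4 to 8; delivery at week 37 to 42)

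- Shortest interval from last application to delivery: (37 − 8) × 7 = 203 days. Longest: (42 − 4) × 7 = 266 days.
- Beyond the window: 203 − 30 = 173 days to 266 − 30 = 236 days.
- The window closes at week 4 + 30/7 = 8.3 or 8 + 30/7 = 12.3. A pregnancy loss before that point is tabulated; a later one is not.

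**Frequency** (assumptions: 20 to 60 of about 200 subjects are women of childbearing potential; the contraceptive failure rate of below 1% in Protocol 6.1, given without a time unit, is taken as 1% per year)

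- Expected pregnancies in 12 months: 20 × 0.01 = 0.2 to 60 × 0.01 = 0.6.
- Chance of at least one pregnancy: 1 − exp(−0.2) = 18% to 1 − exp(−0.6) = 45%.
- Only some pregnancies would lead to a late SAE, so the chance of one is lower than this.
- Weight of one omitted subject: 1/200 = 0.5 percentage points, or 1/100 = 1 point if 100 are treated.

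**The case against.** The SAP is open about its rule. It governs over the protocol, says that data outside the window will be listed, and promises a listing of all SAEs with a flag. In a single-arm descriptive study of at most about 200 subjects, one flagged line tells a reader nearly as much as a table row with a count of one. A 30-day cut-off roughly matches the clinical-database capture period in Protocol 11.1.6, so all reported SAEs could be read as those in that database. Related late SAEs still go to the safety database, and unexpected related ones to authorities and sites (Protocol 11.1.8).

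Most of this stands. It shows that the 30-day definition is reasonable and that the signal is not lost. It does not supply the summary promised in Protocol 12.7.2. The match of periods is also only approximate, given the minimum wording in 11.1.2 and the follow-up visit timed from the Exit Visit.

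A reader might infer that a birth defect would be missing from the tables because of the 30-day rule. The documents do not support that. The Safety population is patients who applied the gel, and neither document says under whom an SAE in a child is tabulated. A late pregnancy loss in the subject herself is the cleaner example.

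A reader might also take 18% to 45% as the chance of an untabulated SAE. It is the chance of any pregnancy, under assumed inputs.

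**Conclusion.** The point holds in limited form. The SAP's SAE tables are narrower than Protocol 12.7.2 at both ends: SAEs before first application and non-fatal SAEs after last application + 30 days have no summary, and at best a flagged listing. That the SAP hides late SAEs, or that the 30-day TEAE definition is itself wrong, would go beyond the documents.

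The size is small. Zero or one late SAE is likely by the pregnancy route. That rests on the assumed number of women of childbearing potential and on reading the failure rate as annual; neither is in the documents. The number of pre-dose SAEs, or of late SAEs by other routes, cannot be estimated from the documents. All analyses are descriptive (SAP 6.1.1.1), so no test or decision rule changes. It is still worth correcting, because it concerns the primary objective and costs little.

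**What to change.** In SAP 6.4.2.4:

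1. Keep both treatment-emergent SAE tables, and the TEAE rows in 6.4.2.1, unchanged.
2. Add one separate summary of SAEs outside the on-treatment period, in two blocks (before first application; after last application + 30 days), by SOC, PT, severity and relationship. Do not pool it with the treatment-emergent tables. Up to day 30 all SAEs are reportable. Afterwards, apart from any days left before the last study visit, only related ones must be reported (Protocol 11.1.6). Pooling would mix the two and could inflate the related share.
3. Footnote that difference in reporting.
4. Fill the summary after reconciling the clinical database with the safety database before lock.
5. State that pregnancy-outcome SAEs are counted under the exposed subject.

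The cost is a few sentences of SAP text, one small table and one reconciliation. The downside is that late ascertainment is incomplete, which a separate display makes visible. Outcomes reported after lock remain in the safety database only. The treatment-emergent SAE tables would still have no severity breakdown, which Protocol 12.7.2 also promises; the sponsor could add it or state that the listing serves that purpose.
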